## 8.5. Interim Monitoring Plan

A formal interim analysis of efficacy will be conducted when 50% of events (i.e., information fraction = 0.50) have been observed; i.e., we will conduct an interim analysis to compare the two treatment arms when 40 participants enrolled on this trial have a reported progression to Stage 2 or 3 T1D. To preserve the Type I error rate control for each of these comparisons on superiority, the Lan-DeMets error spending rate function with the O'Brien-Fleming boundaries is utilized. If these boundaries are crossed, then the TrialNet DSMB will determine if accrual to that arm should be suspended and/or if treatment of participants should be modified based on these results. The interim and final analysis boundaries and characteristics were generated using the East 6 clinical trial software program (version 6.3, Cytel Inc).

Information fraction	Cumulative events	Alpha spent	Efficacy boundary (p-value)
0.50	40	0.0031	2.963 (or -2.963)
1.00	80	0.00153	1.969 (or -1.969)

The DSMB may terminate the trial prematurely if a statistically significant effect is observed and it is considered that all major trial objectives have been met.

In lieu of a formal futility rule at the interim analysis (i.e., 50% information), we will utilize conditional probability methods to assess the probability that hydroxychloroquine will delay time to T1D stage progression based on the data observed at that point if the observed hazard ratio is  $>1.05$  (i.e., in favor of placebo).

The DSMB will also consider early termination due to absence of a treatment effect (i.e., futility) based on computations of conditional power conducted both under the initial study design and under the current trend of the data.

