Criteria for diabetes_onset (T1DM) are based on glucose testing, or the presence of unequivocal hyperglycemia with acute metabolic decompensation (diabetic ketoacidosis). One of the following criteria must be met on two occasions as soon as possible but no less than one day apart for diabetes to be defined: 1. Symptoms of diabetes plus casual plasma glucose concentration ≥ 200 mg/dL (11.1 mmol/L). Casual is defined as any time of day without regard to time since last meal. The classic symptoms of diabetes include polyuria, polydipsia, and unexplained weight loss. 2. Fasting plasma glucose ≥ 126 mg/dL (7 mmol/L). Fasting is defined as no caloric intake for at least 8 hours. 3. 2 hour plasma glucose ≥ 200 mg/dL (11.1 mmol/L). The test should be performed using a glucose load containing the equivalent of 1.75g/kg body weight to a maximum of 75g anhydrous glucose dissolved in water. It is preferred that at least one of the two testing occasions involve an OGTT. Cases identified will be confirmed as having diabetes if the glucose values to make these determinations were obtained in a TrialNet laboratory as part of an OGTT. Cases diagnosed with diabetes by symptoms and casual glucose ≥ 200 mg/dL or by other criteria than the above will be adjudicated by the TrialNet Endpoint Adjudication Committee.

The date of arriving at the study endpoint is the date of the second occasion that meets either of the above criteria or the date in which the participant presented in a state of DKA.

3. Primary Analysis

The study design is a randomized double-blind placebo-controlled trial. The primary objective of the study is to assess the effect of hydroxychloroquine versus placebo on the risk of developing abnormal glucose tolerance (AGT) as measured from an OGTT.

The cumulative incidence of AGT over time since randomization within each treatment group will be estimated from a Kaplan-Meier estimate of the "AGT-free" survival function. Time-to-AGT was discretized to 6-month times in keeping with the OGTT schedule. The difference between groups in the cumulative incidence functions, and the associated hazard functions, will be tested at the 0.05 level, two-sided, using the Cox regression including age as a covariate (1, 5). The critical value for the test statistic, and confidence intervals in this primary analysis will be determined by the group-sequential procedure.

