1. Evidence that the HR is not constant over the period of follow up will be assessed and the risk of diabetes will be assessed in a PH model. The primary test for treatment effect is based on the Cox model, which assumes a proportional hazard between treatment groups. If there is a true treatment effect but it is not proportional over the follow-up period the test will have substantially less statistical power than stated in the statistical section of the protocol. Therefore, to establish a reasonable guide to pursue the possibility of a non-proportional treatment effect we will use the guideline requiring a significance level of 0.10 or less of the LRT from the standard Cox model. Graphical diagnostics using Schoenfeld residuals will be employed to explore evidence for a monotonically decreasing effect of treatment over the follow-up period. Also, plotting the Kaplan-Meier time-to-AGT rates by treatment group on the log-log scale will provide visual assessment of any diminishing effect of treatment (equal distance separation of curves indicates proportional hazard). We will characterize any such decreasing effect of treatment by model parameterization with monotonically decreasing benefit over the follow-up time. Initially, a treatment interaction with log-transformed time-on-study will be fit to the data and the log likelihood improvement in the fit noted. Other time transforms will be explored only to characterize mathematically the rate of the diminishing effect. Of particular interest will be characterizing the point in follow-up where the hazard ratio is 1. Any variations in proportional hazards other than a monotonically decreasing effect will not be of interest because of the possibility that it is simply random error.

5. Study Power and Sample Size

This study has been designed to provide 83% power to detect a 50% risk reduction in the hazard rate for progression to Stage 2 or 3 T1D (abnormal glucose tolerance or diabetes diagnosis) using a two-sided test at the 0.05 level after a minimum of two years of follow-up on all participants and an expected total study duration (accrual and follow-up) of six years. We note that if accrual is more rapid than expected, minimum follow-up on participants may need to be extended in order to meet the number of events required for the final analysis.

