A total of 201 participants will be randomized in a 2:1 allocation to treatment with hydroxychloroquine (n=135) vs. placebo (n=66). Randomization will be conducted using block randomization with variable block sizes with stratification on (1) whether or not participants have been previously treated for T1D prevention, and (2) age group (< 8 years old vs. 8 years old or older).

The assumptions underlying the estimated sample size for this design are: (1) 40% two-year event rate in the placebo group, (2) detectable hazard ratio of 0.50 (i.e. 22.5% two-year event rate) in the hydroxychloroquine group, (3) less than a 10% two-year dropout rate in both groups, and (4) survival curves which are consistent with exponential survival distributions. Even testing for variable proportions of each stratum and with slight variation in the expected hazard rates for the placebo group across the strata, our proposed sample size of 201 participants will provide at least 83% power to detect a hazard ratio of 0.50 in the time to T1D stage progression between the two treatment groups using a stratified Cox regression model⁷⁵.

Under the above assumptions, the target total number of events is equal to 80; i.e., the final analysis will be conducted once 80 events (confirmed abnormal glucose tolerance, diabetes) have been observed. If the accrual rate is 50 patients per year, with the above assumptions it is estimated that the enrollment period will last approximately 4 years with a total study duration of approximately 6 years (4 years of accrual + minimum of 2 years of follow-up) to provide a sufficient number of events to detect the assumed difference.

The final test of significance up to the six-year time point will employ group sequential critical values to protect against inflation in the type I error probability due to interim assessments of the emerging data for review by the DSMB (see Section 8.5).

Note the accrual period and the study sample are only projections, since the actual accrual rate and the loss-to-follow-up rate are unknown. As the study progresses, more accurate projections of the study end date will be computed based on the observed rate of enrollment, the observed number of events, and the observed rate of loss-to-follow-up. These data will be provided to the DSMB and the TrialNet governing body, and if need be, this document will be amended.

6. Interim Monitoring Plan

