A formal interim analysis of efficacy will be conducted when 50% of events (i.e., information fraction = 0.50) have been observed; i.e., we will conduct an interim analysis to compare the two treatment arms when 40 participants enrolled on this trial have a reported progression to Stage 2 or 3 T1D. To preserve the Type I error rate control for each of these comparisons on superiority, the Lan-DeMets error spending rate function with the O'Brien-Fleming boundaries is utilized. If these boundaries are crossed, then the TrialNet DSMB will determine if accrual to that arm should be suspended and/or if treatment of participants should be modified based on these results⁷⁶. The interim and final analysis boundaries and characteristics were generated using the East 6 clinical trial software program (version 6.3, Cytel Inc).

Information fraction	Cumulative events	Alpha spent	Efficacy boundary (p-value)
0.50	40	0.0031	2.963 (or -2.963)
1.00	80	0.00153	1.969 (or -1.969)

The DSMB may terminate the trial prematurely if a statistically significant effect is observed and it is considered that all major trial objectives have been met.

In lieu of a formal futility rule at the interim analysis (i.e., 50% information), we will utilize conditional probability methods to assess the probability that hydroxychloroquine will delay time to T1D stage progression based on the data observed at that point if the observed hazard ratio is >1.05 (i.e., in favor of placebo).

The DSMB will also consider early termination due to absence of a treatment effect (i.e., futility) based on computations of conditional power conducted both under the initial study design and under the current trend of the data⁷⁷.

7. General Considerations

1. Analysis Populations

The Intention to Treat Population (ITT)

The intention to treat population comprises all randomized (as planned) subjects.

Full Analysis Population

The Full Analysis Set (FAS) will comprise all subjects who received any study drug and who participated in at least one post-baseline assessment. These will be analyzed as randomized. FAS will be the primary efficacy population. So, FAS is a subset of ITT.

Per Protocol Population

The Per Protocol Set (PPS) will comprise all subjects who did not substantially deviate (defined as greater than or equal to 75% protocol compliance) from the protocol as to be determined on a per-subject basis before data base lock and unblinding.

Safety Population

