All subjects who received any study treatment (including control) but excluding subjects who drop out prior to receiving any treatment.

2. Timing of Analyses

The final analysis will come after the total number of events (confirmed abnormal glucose tolerance) in the placebo group is between 64 and 70. This will result in detectable hazard ratios of 0.496 to 0.512 to achieve the planned 80% statistical power when testing at the 0.05 level (2-sided) for the primary analysis.

3. Missing Data

In general, missing values will be assumed to be *missing completely at random (MCAR)* unless empirical evidence to the contrary can be established internal to the study. The methodology employed in analyzing time-to-T1D utilizes whatever follow-up has been recorded for each subject (i.e., maximum utilization of follow-up time). Presuming no evidence against MCAR no methods will be employed to impute additional follow-up of subjects that drop out (i.e., lost to follow-up). All secondary endpoints will use the complete-case analysis approach which limits the analytical cohort to those subjects that have the secondary endpoint of interest measured and recorded. In modeling to adjust for risk factors associated with the endpoint (i.e. covariates), missing values will be assigned the mean from the known covariate cohort. This simple rule will be employed only if the percent missing is less than 10% for the analytical cohort. If the missing is 10% to 20% a separate indicator for missing will be included in the modeling. If the missing in exceeds 20% the covariate will be removed from consideration.

8. Safety Analyses

Safety will be evaluated with summary of adverse events for the safety population. The following parameters will be assessed during the study:

Adverse Events

The summary statistics will be produced in accordance with Section 8. Treatment emergent adverse events (AEs) are those events that occur after the baseline assessment. Only Grade 2 or greater adverse events were reported in this study. The incidence of the following AEs will be reported:

A tabular summary of AE will present: Number of subjects with any AE; Number of SAEs with outcome death; Number subjects with SAE; Number subjects with AEs leading to discontinuation of study drug, even if by protocol; Number of subjects with AEs leading to discontinuation of study; Total number of AEs; Total number of SAEs [TABLE].

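### SAP 7 times the final analysis at 64–70 placebo-arm events with 80% power, against the plan's 80 total events with 83% power

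*SAP*

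**What the plan says.** SAP section 7 (General Considerations), item 2, is the section devoted to timing. It states: "The final analysis will come after the total number of events (confirmed abnormal glucose tolerance) in the placebo group is between 64 and 70". It continues: "This will result in detectable hazard ratios of 0.496 to 0.512 to achieve the planned 80% statistical power", at the two-sided 0.05 level.

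SAP section 5 (Study Power and Sample Size) gives another rule: "the final analysis will be conducted once 80 events (confirmed abnormal glucose tolerance, diabetes) have been observed". Its power statement is: "This study has been designed to provide 83% power to detect a 50% risk reduction in the hazard rate". Protocol 3.9.1 and 8.4 give the same 80 events and 83%. SAP section 5 and Protocol 8.4 plan 201 participants, 135 on hydroxychloroquine and 66 on placebo.

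The monitoring plan is built on the 80-event rule. SAP section 6 says: "A formal interim analysis of efficacy will be conducted when 50% of events (i.e., information fraction = 0.50) have been observed". Protocol 8.5 gives the count: "we will conduct an interim analysis to compare the two treatment arms when 40 participants enrolled on this trial have a reported progression". The tables in both sections put 80 cumulative events at information fraction 1.00.

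**The concern.** The two rules disagree on three things.

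| | SAP 7, item 2 | SAP 5; Protocol 3.9.1 and 8.4 |
|---|---|---|
| Arm counted | placebo only | both arms |
| Events | 64 to 70 | 80 |
| Planned power | 80% | 83% |

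No section says which one governs, and the conflict lies inside the SAP itself as well as between the SAP and the protocol. At stake is whether the cut-off for the single confirmatory analysis can be shown to have been fixed in advance. Item 2 also gives a range, which leaves discretion over the exact cut-off. And a placebo-only count would require event counts by arm in a double-masked trial.

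**Working it through.** **Inputs from the plan (SAP 5; Protocol 3.9.1 and 8.4).** 135 versus 66 participants; two-year placebo event rate 40%; hazard ratio (HR) 0.50; exponential event times; accrual 50 per year; two-year dropout below 10%; two-sided 0.05.

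**Assumptions added.** Uniform accrual over 201/50 = 4.02 years with cut-off at 6.02 years, and a constant dropout hazard that continues after year two. The plan gives only an upper limit for dropout, so 0–10% is shown.

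**1. The 80-event rule reproduces.** Schoenfeld: power = Φ(√(D·p(1−p))·|ln HR| − z), where D is total events and p the fraction allocated to one arm.
- D = 80, p = 2/3: √(80 × 2/9) × 0.6931 = 2.923. Then 2.923 − 1.960 = 0.963 and power = 83.2%.
- With the plan's final critical value of 1.969: 83.0%.
- With the 135:66 split: 82.9%, or 82.7% with 1.969.

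The stated 83% is right for 80 total events at 2:1.

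**2. The hazard ratios in item 2 come from 1:1 allocation.** Detectable HR at 80% power = exp(−(1.960 + 0.8416)/√(D·p(1−p))).

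| Total events | 1:1 | 2:1 | 135:66 |
|---|---|---|---|
| 64 | exp(−2.8016/4.000) = 0.496 | exp(−2.8016/3.771) = 0.476 | 0.474 |
| 70 | exp(−2.8016/4.183) = 0.512 | exp(−2.8016/3.944) = 0.491 | 0.490 |

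The printed 0.496 and 0.512 match the 1:1 column exactly, with 64 and 70 as totals over both arms. They match neither this trial's allocation nor a placebo-only count.

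**3. The placebo-only count against the arm size.** 64/66 = 97.0% and 70/66 = 106.1%. Counts of 67–70 exceed the planned arm; 64–66 need nearly every placebo participant to progress.

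**4. Placebo events expected under the plan.** Placebo hazard λ = −ln(0.6)/2 = 0.2554 per year; dropout hazard m = −ln(1−d)/2, where d is two-year dropout. With no dropout, the expected count at 6.02 years is 66 × [1 − (e^(−2λ) − e^(−6.02λ))/(4.02λ)] = 66 × [1 − (0.6000 − 0.2149)/1.0268] = 41.2. The ceiling with unlimited follow-up is 66·λ/(λ+m).

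| Two-year dropout | Placebo events at 6.02 years | Placebo events when 80 total are expected | Ceiling, unlimited follow-up |
|---|---|---|---|
| 0% | 41.2 | 35.6 | 66.0 |
| 2% | 40.5 | 35.6 | 63.5 |
| 5% | 39.5 | 35.6 | 60.0 |
| 10% | 37.8 | 35.5 | 54.7 |

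The ceiling stays at or above 64 only for two-year dropout up to about 1.6%. Even with no dropout, 64 placebo events would take about 15.9 years from first enrolment, by which time about 176 events in total would be expected.

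**5. If item 2 meant total events.** At HR 0.50 and 2:1, power is 74.3% at 64 events and 78.0% at 70 (74.0% and 77.7% for 135:66). Type I error would barely move. With the interim at 40 events and boundary 2.963, the exact final critical value would be 1.965–1.966. Keeping 1.969 gives a two-sided level of 0.0495–0.0497.

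**The case against.** The best defence is that item 2 is a visible slip that would change nothing in practice. The 80-event trigger is stated in Protocol 3.9.1, Protocol 8.4 and SAP 5 and is built into both interim tables, so a trial team would probably follow it. That is likely, and it limits the practical harm. It does not remove the conflict. Striking the reference to the placebo group still leaves 64–70 against 80, 80% against 83%, and hazard ratios for the wrong allocation. Nor does any section subordinate item 2 to section 5.

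Second, the power loss is not a consequence of the text as written. Read literally, item 2 would wait for far more than 80 events, and power would exceed 83%. This is correct: the literal rule is unworkable, not underpowered, and the 74–78% applies only to the total-event reading.

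Third, 67–70 placebo events are ruled out only if 66 are randomised to placebo, and Protocol 3.9.1 calls the total of 201 approximate. The accurate statement is that the range exceeds the planned arm. Likewise, with almost no dropout, 64 could eventually be reached, but only after about 16 years against a planned six.

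**Conclusion.** The concern holds, and item 2 must be corrected. The contradiction on arm, count and power can be read directly from the text and needs no modelling; the same is true of the 64–70 range against a planned arm of 66. The 1:1 origin of the hazard ratios follows from the Schoenfeld formula alone. The modelled figures (about 36 placebo events at the 80th total event, 38–41 at six years) rest on the plan's event rate, hazard ratio and accrual, plus uniform accrual and constant dropout of 0–10% per two years. The damage is to the pre-specification of the final analysis. A power loss to 74–78% would arise only if 64–70 were applied as a total; the effect on type I error is negligible.

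**What to change.** Delete the 64–70 placebo-event rule, the hazard ratios 0.496–0.512 and the 80% power figure from SAP section 7, item 2. Replace them with, for example:

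> The final analysis takes place at the 80th confirmed primary event (abnormal glucose tolerance or diabetes), counted over both arms. With 2:1 allocation this gives 83% power at a hazard ratio of 0.50 (Section 5). The critical value is that of the group-sequential procedure in Section 6.

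This costs SAP wording only: no added participants, no new sample size, and no change to the looks at 40 and 80 events.

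One related correction is separate. SAP section 3 also frames the primary objective by abnormal glucose tolerance alone ("on the risk of developing abnormal glucose tolerance (AGT) as measured from an OGTT"), whereas the primary outcome in SAP section 2 includes diabetes. Editing item 2 does not cure that.

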As illustrated in Figure 2, data also suggest that the rate of progression through each stage is age dependent, with younger individuals progressing more rapidly.

Overall, about 40% of individuals at Stage 1 T1D will progress to Stage 2 within two years (Figure 3), and almost 70% of those at Stage 2 will develop clinically overt T1D (Stage 3) within four years (Figure 4). More children than adults will be expected to progress from Stage 1 to 2 and from Stage 2 to Stage 3 during these time periods.

[figure not shown]

FIGURE 3: Two year risk of confirmed abnormal glucose tolerance is 38% among individuals with multiple autoantibody positivity and normal glucose tolerance at baseline in the TN01 Pathway to Prevention Study.

[figure not shown]

Figure 4: Four year risk of diabetes onset is 68% among individuals with multiple autoantibody positivity and confirmed abnormal glucose tolerance in the TN01 Natural History/Pathway to Prevention Study.

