 6= May include samples for pharmacokinetic assessment, RNA, plasma, serum, DNA, measures of B and T cell number and function to understand the effect of therapy on the immune system and infectious disease. The schedule for these assessments may vary as appropriate. At no time will the blood draw volume exceed what is allowable according to the participant’s age and body weight (For participants <18 years, 5 mL/kg per visit, 9.5 mL/kg in an 8 week period). Responses to clinically indicated immunizations may be determined through analysis of pre- and post-dose samples.  
 7= Ophthalmology examination: baseline examination may occur any time from screening until three months after randomization. Subsequent examinations will occur annually for all participants, starting at the 12 month visit.  
 8 = All subjects may have interim contact with study personnel for formal inquiry about adverse events and presence or absence of diabetes related symptoms. This interim contact does not require an in-person visit.

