Data from the TrialNet Pathway to Prevention Study may be used to determine participant eligibility. Outcomes from other studies may be used in meta-analyses, but not in the evaluation of this study's efficacy.

4. Secondary Outcomes and Analyses

4.1 Subgroup analyses.

Subgroup analyses will be conducted comparing the effects of hydroxychloroquine versus placebo on the risk of AGT with a test of the group by subgroup factor interaction in a Cox proportional hazard (PH) Model. Subgroups of the population by age (classified appropriately), gender, race/ethnicity (white, nonwhite and Hispanic yes/no), and specific antibody status at baseline. Differences in the treatment effect between subgroups will be tested using Likelihood Ratio Test (LRT) in a Cox PH model (1).

4.2 Covariate analyses.

Similar analyses will be conducted using the values of quantitative baseline factors. They include age, weight, BMI, HbA1c, HLA (DR3/4 vs. others), autoantibody titers, basal C-peptide, stimulated C-peptide (peak and AUC), glucose (fasting, 2-hour, AUC and measures of insulin secretory rate (0-30 min) and sensitivity (ISI) (6,7) modeled from the OGTT) at study entry. The dependence of the treatment effect on the quantitative levels of a covariate will also be assessed by a covariate by treatment group interaction in a PH model. The ISI can also inform on the treatment effect independent of C-peptide.

The association of demographic, genetic, immunologic, metabolic, and lifestyle factors, the presence of illness and concomitant meds, both at baseline and over time, with the risk of AGT onset will be assessed in Cox PH Models over time. The effects of changes in longitudinal factors on AGT risk will be assessed using time-dependent covariates for these factors.

Using a step-up procedure additional covariates will be tested and included in the model only if they improve the log-likelihood at 0.10 level (2-sided). This will be accomplished with the treatment assignment variable included but the inclusion/exclusion of the candidate covariates will be completely independent of the treatment variable's impact on the model. The LRT associated with treatment variable in the full, adjusted model will be used for the test of treatment effect described in the previous paragraph. Thus, the adjustment of the significance level, as with multiple testing, is unnecessary.

4.3 Longitudinal analyses.

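### Cohort-mean filling of missing covariates (SAP 7, item 3) biases age-adjusted marker effects and, if used for missed visits, marker-change effects in the secondary covariate analyses

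*SAP*

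**What the plan says.** SAP 7, item 3 (Missing Data) sets one rule for covariates in risk models: "missing values will be assigned the mean from the known covariate cohort". The mean is not conditional on age, sex, arm or visit. The rule is capped: "This simple rule will be employed only if the percent missing is less than 10% for the analytical cohort". Above that, "If the missing is 10% to 20% a separate indicator for missing will be included in the modeling", and beyond 20% the covariate is dropped. Missing values are taken as missing completely at random (MCAR) "unless empirical evidence to the contrary can be established internal to the study".

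The rule serves SAP 4.2. On the baseline covariates, that section says: "They include age, weight, BMI, HbA1c, HLA (DR3/4 vs. others), autoantibody titers, basal C-peptide, stimulated C-peptide (peak and AUC), glucose", followed by OGTT-based secretion and sensitivity measures. It also uses factors over time: "The effects of changes in longitudinal factors on AGT risk will be assessed using time-dependent covariates for these factors". Candidates enter by a step-up rule at the 0.10 level.

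Protocol 3.3.1 admits participants from age 3 with no upper limit. Protocol 2.1.2 states that "the rate of progression through each stage is age dependent, with younger individuals progressing more rapidly". Age group is a randomisation stratum (Protocol 3.6 and 8.4), so age is known for everyone.

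**The concern.** Several SAP 4.2 covariates, such as weight, BMI and C-peptide, can be expected to vary with age over this range. A child with a missing value receives the average of the whole cohort. In a model that also contains age, such a filled value breaks the link between marker and age. The marker's own effect is diluted, and the part that was lost moves into the age coefficient.

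The problem is sharper for time-dependent covariates. If a missed visit takes the cohort mean, a participant whose own level is far from that mean shows a false jump and then a false return. Those movements are noise added to the changes that SAP 4.2 wants to relate to risk.

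At stake are the secondary answers on which markers, and which marker changes, predict progression.

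**Working it through.** **1. The design figure, and why it is not touched.** Inputs from SAP 5: 80 events, hazard ratio 0.50, 2:1 allocation, two-sided 0.05. By Schoenfeld's formula, √(80 × 2/3 × 1/3) × ln 2 = 4.216 × 0.693 = 2.92. Then 2.92 − 1.96 = 0.96, which gives 83.2% power, or 83.0% with the final critical value of 1.969. The stated 83% is reproduced. The SAP 3 primary model contains treatment and age only, so nothing in it is ever filled. In 400 simulated trials of 201 participants with a mean-filled marker added (marker-age correlation 0.6, 10% missing), the average treatment log hazard ratio moved only from −0.693 to −0.688.

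**2. Baseline marker with age in the model, MCAR.** Let r be the marker-age correlation and m the share filled. In the linear-model approximation:

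- marker coefficient ratio = (1 − r²) / (1 − (1 − m)r²)
- shift in age coefficient = b × r × m / (1 − (1 − m)r²), where b is the true marker effect

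With m = 0.09 (just under the cap):

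| r | ratio | loss |
|---|---|---|
| 0.5 | 0.75 / 0.7725 = 0.971 | 3% |
| 0.7 | 0.51 / 0.5541 = 0.920 | 8% |
| 0.8 | 0.36 / 0.4176 = 0.862 | 14% |

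Cox simulation agrees: 0.388 to 0.376 at r = 0.5 (3%), and 0.384 to 0.334 at r = 0.8 (13%). At m = 0.05 the ratios are 0.984 for r = 0.5 and 0.954 for r = 0.7. A regression fill on age gave 0.387 at r = 0.5 and 0.385 at r = 0.8, so it restored the full-data values.

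**3. Age coefficient.** With r = 0.8, m = 0.09 and b = 0.40, the shift is 0.40 × 0.8 × 0.09 / 0.4176 = 0.069, so an age effect of −0.50 becomes −0.43. With b = −0.40 the shift reverses and −0.50 becomes −0.57. Cox simulation at r = 0.6 and 10% missing shows both directions: −0.400 to −0.366 for a risk-raising marker, and −0.402 to −0.433 for a risk-lowering one.

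**4. Marker without correlated covariates, MCAR.** For a marker uncorrelated with age, the effect was 0.394 on full data and 0.392 after filling. With age left out of the model, it was 0.369 and 0.367. There is no attenuation.

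**5. Missingness concentrated in the youngest quarter** (10% overall, r = 0.6). The marker went from 0.388 to 0.336 (13% loss) and age from −0.400 to −0.315. Imputation conditional on age, arm and outcome gave 0.377 and −0.391.

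**6. Visit-to-visit change.** Let ρ be the within-person correlation between adjacent visits and m the share of visits filled with the cohort mean. The ratio is (1 − ρ) / [(1 − m)(1 − ρ) + m]. With m = 0.09:

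| ρ | ratio | loss |
|---|---|---|
| 0.6 | 0.4 / 0.454 = 0.881 | 12% |
| 0.8 | 0.2 / 0.272 = 0.735 | 26% |
| 0.9 | 0.1 / 0.181 = 0.552 | 45% |

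For change from baseline, a simulation with 10% of visits missing gave 0.404 to 0.202 when the final-visit change SD was half the between-person SD, and 0.389 to 0.322 when the two were equal. The effect of the current level, as opposed to change, was preserved (0.405 to 0.403).

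**7. Treatment-by-marker interaction.** Full data against mean fill gave 0.282 against 0.280, and 0.331 against 0.336. There is no attenuation.

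**The case against.** **The size is modest.** At r = 0.6 and 201 participants the marker bias was −0.024 (0.411 to 0.387) against a standard error of about 0.13. Larger figures need stacked assumptions. With r = 0.8 and 9% missing confined to the youngest quarter, 0.40 falls to 0.29 and the chance of passing the 0.10 step-up test falls from 76% with full data to 59%. The achievable comparator, filling from age, is 71%. This objection stands and sets the severity.

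**Little may be missing at baseline.** Entry needs a recent OGTT, recent autoantibodies and a screening weight (Protocol 3.3.1), and HbA1c is scheduled at screening (Appendix 2). This also stands. A reader might infer age-related missingness from footnote 6 of Appendix 2: "At no time will the blood draw volume exceed what is allowable according to the" age and weight of the participant. That footnote belongs to the mechanistic-assessment row. It does not show that SAP 4.2 baseline covariates go missing in small children.

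**Time-varying values are not mentioned.** SAP 7 item 3 refers to neither visits nor time-dependent covariates, so their coverage is inferred. But no other covariate rule appears in the SAP, and the complete-case sentence concerns secondary endpoints. Either the mean applies or there is no rule, and both call for a sentence.

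**MCAR may be set aside on contrary evidence.** That is so, but no alternative method is named, and the bias in steps 2 and 6 arises under MCAR itself.

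A fractional value for the two-level HLA factor looks odd but is computationally valid, so it adds little.

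**Conclusion.** The point holds for main effects of age-correlated markers in models containing age, and for effects of marker change if the rule is applied to missed visits. The baseline loss is about 3 to 13% (up to 14% by the closed form) for r of 0.5 to 0.8 at 9% missing at random. The change-effect loss is about 12 to 45% for ρ of 0.6 to 0.9 at 9% of visits. These rest on assumed correlations, marker effects and missingness.

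Three stronger readings are tempting and are not supported:

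- That age effects are pulled toward zero in general. Age is never filled, and its coefficient can move either way (step 3).
- That effect modification is diluted. The simulated interactions were unchanged (step 7).
- That every covariate effect is attenuated. Under MCAR, a marker modelled without correlated covariates is not (step 4).

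The primary test, its power and the randomised treatment estimate are essentially unaffected. Severity is minor, and the correction is cheap.

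**What to change.** In SAP 7, item 3:

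- Replace the cohort mean for missing baseline covariates by a single regression prediction from age, sex and the other complete baseline values. This works with the existing step-up selection and likelihood ratio tests. Keep age in any model that uses a value filled this way, because otherwise the prediction carries age's own effect into the marker coefficient.
- State that a missing time-dependent value takes the participant's own last observed value or a within-person model prediction, not the cohort mean.
- Optionally, add multiple imputation including arm and outcome as a sensitivity analysis. It is better not made the main method, because it would need pooled likelihood ratio tests and a rule for stepwise selection across imputed data sets.

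The cost is a few sentences and slight extra programming, with no new data. Single imputation slightly understates standard errors, as the present rule also does.
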